12.4 Confidence intervals

Regardless of results in hypothesis testing, the calculated ratios and differences in between-group comparisons will be complemented with confidence intervals (usually at 95% level but 90% for non-inferiority studies), for descriptive purpose. For the quantitative outcomes, confidence intervals will be based on t-test. For binary outcomes, the confidence intervals will be based on binomial distribution.

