12.6 Covariate adjustment

The final decision on the use of covariates in main analyses will be decided based on preliminary analyses on the final dataset that includes information on the clustering of participants in the same group but does not provide information on the actual intervention delivered to each group.

At this stage, four different regression models for change in LAZ will be constructed, first of these with no covariate adjustments and models 2-4 with various adjustments. If the pointestimates for the regression co-efficient for the intervention group differ in any of the models by more than 10% from that in the unadjusted analyses, the adjusted analysis will be primarily presented in the eventual publications. If all the differences are smaller than 10% (Maldonado & Greenland, 1993), the results in the tables will be shown without covariate adjustments, but model 4 results will be provided in the text as supplementary information.

The four models include:

- 1. No covariate adjustment
- 2. Adjustment for baseline LAZ-score
- 3. Adjustment for baseline WHZ-score
- 4. Adjustment for baseline LAZ-score and baseline WHZ-score and for any of the variables presented in tables 1a and 1b showing statistically significant association (at p<0.1 level) with the change in LAZ-score

13 Storage and release of data

The data meta-data will be stored in a tailor-made hierarchical database, consisting of a MS Access front-end and MySQL tables in the back-end. The database, associated metadata, and form –specific do-files that contain all cumulative data corrections for the respective data collection forms are stored at a computer server at the University of Tampere and daily copied to

a server at the Mangochi research site, University of Malawi. A study statistician ([name]) acts as the manager for these data.

When an investigator wishes to perform certain analyses, s/he will request the respective data from the above-indicated data manager. The data manager will export all the data from the respective data collection form into an excel or Stata file, run the cumulative data correction do-file and then provide the corrected data, together with the syntax for the correction do file (that documents all the completed data editions) to the person requesting the data.

The databases and the do-files will be named with systematic naming format and stored at the central server at the University of Tampere. For each article, the following files will be stored:

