All the above analyses will primarily cover the period from enrolment (when the participants are 6 months old) to the end of the intervention (when the participants are 18 months old).

6. Presentation of the study findings and hypothesis testing

6.1 Comparison of the anthropometric measurements at 18 months of age between intervention groups versus the control group

The group means and standard deviations for length (cm), weight (in kg), MUAC (cm), head circumference (cm) and LAZ, WAZ, WHZ, MUAC z-score and head circumference z-score (in z-score units) will be presented as indicated in Table 1. Group means and standard deviations for the change in anthropometric measurements and z-scores and their 95% confidence intervals between the control group and each of the intervention groups will be presented in Table 2.

Mean in anthropometrics, Z-score and change in measurements in each of the intervention groups will be individually compared against that of the control group using a two-sample t-test. The Holm's method will be used to adjust for the multiple comparisons (Aickin & Gensler,

1996). The raw P-values are presented in tables but the text and conclusion will be based on the Holm-adjusted P-values.

The null-hypothesis of LNS having no impact on linear growth is rejected for each comparison that yields a Holm's adjusted p-value <0.05.

6.3 Incidence of various forms of undernutrition at a single time point The analysis will compare proportions demonstrating various forms of undernutrition at age 18 months (Table 3). Global null hypotheses of no differences between groups and pair-wise comparisons will be tested by Fisher's exact test. Pair-wise comparisons of intervention to control will be done if global null hypothesis is rejected with P<0.05. Participants who had the condition initially will be excluded from the analysis of that form of undernutrition.

7. General notes on statistical methods

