7.6 Covariate adjustment

The same adjustments will be done as for the main analyses.

8. References

9. Legends to the figures

Figure 1. Mean length-for-age z-score at 6, 12 and 18 months by intervention group

10. Figures

Figure 1. Mean length-for-age z-score at 6, 12 and 18 months by intervention group

11. Tables

Table 1 Comparison in	anthropometric in	n the interventior	groups at 1	8 months

Variable	Control	10g milk I NS	20g milk I NS	20g milk- free L NS	40g milk I NS	40g milk- free I NS
				II CE LINS		II CE LINS
Mean weight (SD)	xx.x (xx.x)	XX.X (XX.X)	XX.X (XX.X)	XX.X (XX.X)	xx.x (xx.x)	xx.x (xx.x)
Raw p-value for intervention compared to control		x.xxx	x.xxx	X.XXX	x.xxx	X.XXX
Mean length (SD)	xx.x (xx.x)	xx.x (xx.x)	XX.X (XX.X)	xx.x (xx.x)	xx.x (xx.x)	xx.x (xx.x)
Raw p-value for intervention compared to control		x.xxx	x.xxx	X.XXX	x.xxx	X.XXX
Mean middle upper arm circumference (SD)	xx.x (xx.x)	XX.X (XX.X)	XX.X (XX.X)	XX.X (XX.X)	xx.x (xx.x)	xx.x (xx.x)
Raw p-value for intervention compared to control		x.xxx	x.xxx	X.XXX	x.xxx	X.XXX
Mean head circumference (SD)	xx.x (xx.x)	xx.x (xx.x)	xx.x (xx.x)	XX.X (XX.X)	xx.x (xx.x)	xx.x (xx.x)
Raw p-value for intervention compared to control		x.xxx	x.xxx	x.xxx	x.xxx	X.XXX
Mean Weight-for-age z-score (SD)	xx.xx (xx.xx)	XX.XX (XX.XX)	XX.XX (XX.XX)	xx.xx (xx.xx)	xx.xx (xx.xx)	xx.xx (xx.xx)
Raw p-value for intervention compared to control		X.XXX	X.XXX	X.XXX	X.XXX	X.XXX
--	---------------	------------------	------------------	------------------	------------------	------------------
Mean Length-for-age z-score (SD)	xx.xx (xx.xx)	XX.XX (XX.XX)	XX.XX (XX.XX)	XX.XX (XX.XX)	XX.XX (XX.XX)	XX.XX (XX.XX)
Raw p-value for intervention compared to control		X.XXX	X.XXX	X.XXX	X.XXX	X.XXX
Mean Weight-for-length z-score (SD)	xx.xx (xx.xx)	XX.XX	XX.XX	XX.XX	XX.XX	XX.XX
		(xx.xx)	(xx.xx)	(xx.xx)	(xx.xx)	(xx.xx)
Raw p-value for intervention compared to control		X.XXX	X.XXX	X.XXX	X.XXX	X.XXX
Mean MUAC z-score (SD)	xx.xx (xx.xx)	XX.XX	XX.XX	XX.XX	XX.XX	XX.XX
		(xx.xx)	(xx.xx)	(xx.xx)	(xx.xx)	(xx.xx)
Raw p-value for intervention compared to control		x.xxx	X.XXX	X.XXX	X.XXX	X.XXX
Mean head circumference z-score (SD)	xx.xx (xx.xx)	XX.XX	XX.XX	XX.XX	XX.XX	XX.XX
		(xx.xx)	(xx.xx)	(xx.xx)	(xx.xx)	(xx.xx)

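### SAP Appendix 1 tests incident stunting, underweight and wasting by unadjusted Fisher's exact tests and names no regression model for the adjustment it promises, which gives up power that the 6-month Z-score could recover

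*SAP*

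**What the plan says.** Appendix 1 section 6.3 covers severe and moderate-to-severe stunting, underweight and wasting at 18 months. It names one method: "Global null hypotheses of no differences between groups and pair-wise comparisons will be tested by Fisher's exact test". The pair-wise step is gated: "Pair-wise comparisons of intervention to control will be done if global null hypothesis is rejected with P<0.05". Baseline status is used once: "Participants who had the condition initially will be excluded from the analysis of that form of undernutrition". Table 3 of the appendix has a relative risk with 95% interval for each LNS arm and one P-value per outcome.

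Appendix 1 section 7.6 reads in full: "The same adjustments will be done as for the main analyses". The main text, section 12.6, defines those adjustments for a continuous outcome: "At this stage, four different regression models for change in LAZ will be constructed". Model 2 is "Adjustment for baseline LAZ-score", model 3 uses baseline WHZ, and model 4 uses both plus any Table 1a or 1b variable associated with change in LAZ at p<0.1. If any group coefficient moves by more than 10%, the adjusted analysis is presented as primary. Otherwise, "the results in the tables will be shown without covariate adjustments, but model 4 results will be provided in the text as supplementary information".

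Section 7.4 of the appendix refers back to section 12.4, which says: "For binary outcomes, the confidence intervals will be based on binomial distribution".

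**The concern.** Fisher's test accepts no covariate and returns no group coefficient to which a 10% rule could be applied. The adjusted analysis promised in 7.6 therefore needs a regression model for a binary outcome, and Appendix 1 names neither a model nor a link. The SAP makes that choice elsewhere: log-binomial for serious adverse events (section 11.5) and logistic for developmental delay (Appendix 2, section 5.4).

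Among children above the cut-off at 6 months, those who started close to it are the most likely to cross it by 18 months. Using the Z-score only to exclude prevalent cases discards that information for everyone who remains. Two things are at stake. A real reduction in stunting is more likely to be missed. And the analyst has to choose a link later, which can decide which result counts as primary under the 10% rule.

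**Working it through.** The SAP states no rate, SD, correlation or power for these outcomes, so there is no figure to reproduce. The loss was sized by simulation.

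**From the SAP.** 1932 infants and six groups; cut-offs Z < -2 and Z < -3; prevalent cases excluded; 0.05 level.

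**Assumed.** Equal groups, 15% missing, LAZ at 6 months with mean -1.4 and SD 1, mean fall of 0.4 by 18 months, LNS effect 0.2 to 0.3 Z, correlation between 6 and 18 months 0.5 to 0.85, two-sided tests.

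**Children at risk per arm.** 1932 / 6 = 322, and 322 × 0.85 = 273.7. The share at or above -2 is Φ(0.6) = 0.726, giving 199. The share at or above -3 is Φ(1.6) = 0.945, giving 259.

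**Pair-wise power.** One LNS arm against control, 2000 runs per setting, effect 0.25 Z. LR is the likelihood-ratio test from logistic regression; the adjusted model adds baseline LAZ.

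| Cut-off | Correlation | Fisher | Unadjusted LR | Adjusted LR | Adjusted minus Fisher |
|---|---|---|---|---|---|
| -2 | 0.5 | 47.6% | 50.2% | 53.6% | 6.0 |
| -2 | 0.7 | 55.3% | 58.2% | 66.2% | 10.9 |
| -2 | 0.85 | 66.0% | 68.3% | 80.2% | 14.2 |
| -3 | 0.5 | 32.6% | 35.8% | 37.3% | 4.7 |
| -3 | 0.7 | 35.1% | 39.2% | 44.4% | 9.3 |
| -3 | 0.85 | 37.2% | 42.4% | 53.0% | 15.8 |

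Over effects of 0.2 to 0.3 Z the gain runs from 4.5 to 15.8 points. About 2 to 5 points come from Fisher's conservatism (Fisher to unadjusted LR), and the rest from baseline LAZ. At cut-off -3 and correlation 0.5 the baseline value adds only 37.3 - 35.8 = 1.5 points. With no effect, Fisher rejects in 3.8 to 4.6% of runs and the adjusted test in 4.2 to 5.3%.

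A separate simulation, which also tried modified Poisson regression in place of logistic, gave gains of about 2 to 16 points with size near 5%.

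**Check by formula.** Power = Φ{(|p0 - p1| - 1.96 √[2 p̄(1 - p̄)/n]) / √[(p0(1 - p0) + p1(1 - p1))/n]}, with p̄ the mean of p0 and p1. For 28.1% v 18.9% and n = 199: (0.092 - 0.0833) / 0.0423 = 0.206, so 58%; the simulated unadjusted LR gave 58%. For 8.7% v 5.0% and n = 259: (0.037 - 0.0435) / 0.0221 = -0.294, so 38%; the simulation gave 39%.

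**With the six-group gate of 6.3.** All five LNS arms at 0.25 Z, 1000 runs, Pearson chi-square standing in for the 2×6 Fisher test, adjusted analysis by logistic regression. Probability of passing both the gate and a pair-wise test, at correlations 0.5, 0.7 and 0.85:
- cut-off -2: 40% v 41%, 45% v 52%, 58% v 73%
- cut-off -3: 25% v 26%, 23% v 28%, 28% v 37%

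A separate run put the gain after the gate at about 1 to 14 points. With 1000 runs the standard error of one percentage is up to √(0.5 × 0.5 / 1000) = 1.6 points, so the two runs agree.

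**What the link does to the 10% rule.** Large simulated samples with balanced groups (no confounding), effect 0.25 Z. The change is the adjusted over the unadjusted log ratio, minus 1.
- log odds ratio, cut-off -2: -0.461 to -0.498 (8%), -0.504 to -0.590 (17%), -0.611 to -0.810 (33%)
- log odds ratio, cut-off -3: -0.537 to -0.567 (6%), -0.570 to -0.663 (16%), -0.688 to -0.893 (30%)
- log risk ratio: at most 1% in all six settings

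A logistic model would therefore trip the 10% rule at correlations of 0.7 and above through non-collapsibility alone. A risk-ratio model would not.

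**The case against.** A reader might infer that 6.3 and 7.6 contradict each other and cannot both be followed. The documents do not support that. The primary outcome has the same layout: a two-sample t-test in section 11.3, which takes no covariates either, and regression models in 12.6 that displace it only if an estimate moves by more than 10%. A Fisher test with a later regression fits that pattern. One difference remains. A t-test is a linear regression on group, so its adjusted form is obvious, whereas a binary outcome leaves the link open.

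A reader might also infer that the baseline Z-score is ignored. It is not: it defines the exclusion of prevalent cases, and 7.6 calls for adjustment. What is missing is the model. For underweight there is a further gap. Read literally, the carried-over models guarantee LAZ and WHZ but admit WAZ only through a screen on association with change in LAZ.

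It is fair to add that Fisher's test is valid, that these are secondary outcomes, and that the confirmatory analysis is of change in LAZ as a continuous variable. All of that stands and limits the weight of the point. It does not remove the power loss or the unspecified model.

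**Conclusion.** The point holds as an inefficient and under-specified analysis of secondary outcomes. It is neither an internal contradiction nor an invalid test. The loss is about 2 to 16 points of pair-wise power and about 1 to 14 after the global gate: close to nothing after the gate at a correlation of 0.5, and material at 0.7 and above.

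The direction was the same in every setting tried. The size rests on an assumed LAZ distribution, correlation, effect and missingness, and on equal groups. Only stunting was simulated, so no figure here should be read across to underweight or wasting. The gated figures use logistic regression; modified Poisson was checked for the pair-wise tests only.

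**What to change.** In Appendix 1 section 6.3, make the primary test for each binary outcome a modified Poisson regression with robust variance (or log-binomial), so that the estimate is the relative risk of Table 3. Include group and, as a fixed covariate, the continuous 6-month Z-score of the same index: LAZ for stunting, WAZ for underweight, WHZ for wasting. Keep the present order, with a global 5-df test of group followed by pair-wise comparisons with control.

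In section 7.6, state that the 10% change-in-estimate rule of 12.6 does not apply to these outcomes, and in particular not to odds ratios.

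Keep Fisher's exact test for sparse outcomes, under a threshold on total events over all groups that is fixed before unblinding.

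The cost is SAP wording. The baseline values are already measured and already used for the exclusions. The small downside is that a model-based test replaces an exact one.

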7.1 Software

The same as that for the primary outcome analyses

7.2 Preparing anthropometric data for analysis

The same as that for the primary outcome analyses

7.3 Multiple comparisons

The same as that for the primary outcome analyses.

7.4 Confidence intervals

The same as that for the primary outcome analyses.

7.5 Interaction and effect modification

The same as that for the primary outcome analyses.

7.6 Covariate adjustment

The same adjustments will be done as for the main analyses.

8. References

9. Legends to the figures

Figure 1. Mean length-for-age z-score at 6, 12 and 18 months by intervention group

10. Figures

Figure 1. Mean length-for-age z-score at 6, 12 and 18 months by intervention group

11. Tables

Table 1 Comparison in	anthropometric in	n the interventior	groups at 1	8 months

Variable	Control	10g milk I NS	20g milk I NS	20g milk- free L NS	40g milk I NS	40g milk- free I NS
				II CE LINS		II CE LINS
Mean weight (SD)	xx.x (xx.x)	XX.X (XX.X)	XX.X (XX.X)	XX.X (XX.X)	xx.x (xx.x)	xx.x (xx.x)
Raw p-value for intervention compared to control		x.xxx	x.xxx	X.XXX	x.xxx	X.XXX
Mean length (SD)	xx.x (xx.x)	xx.x (xx.x)	XX.X (XX.X)	xx.x (xx.x)	xx.x (xx.x)	xx.x (xx.x)
Raw p-value for intervention compared to control		x.xxx	x.xxx	X.XXX	x.xxx	X.XXX
Mean middle upper arm circumference (SD)	xx.x (xx.x)	XX.X (XX.X)	XX.X (XX.X)	XX.X (XX.X)	xx.x (xx.x)	xx.x (xx.x)
Raw p-value for intervention compared to control		x.xxx	x.xxx	X.XXX	x.xxx	X.XXX
Mean head circumference (SD)	xx.x (xx.x)	xx.x (xx.x)	xx.x (xx.x)	XX.X (XX.X)	xx.x (xx.x)	xx.x (xx.x)
Raw p-value for intervention compared to control		x.xxx	x.xxx	x.xxx	x.xxx	X.XXX
Mean Weight-for-age z-score (SD)	xx.xx (xx.xx)	XX.XX (XX.XX)	XX.XX (XX.XX)	xx.xx (xx.xx)	xx.xx (xx.xx)	xx.xx (xx.xx)
Raw p-value for intervention compared to control		X.XXX	X.XXX	X.XXX	X.XXX	X.XXX
--	---------------	------------------	------------------	------------------	------------------	------------------
Mean Length-for-age z-score (SD)	xx.xx (xx.xx)	XX.XX (XX.XX)	XX.XX (XX.XX)	XX.XX (XX.XX)	XX.XX (XX.XX)	XX.XX (XX.XX)
Raw p-value for intervention compared to control		X.XXX	X.XXX	X.XXX	X.XXX	X.XXX
Mean Weight-for-length z-score (SD)	xx.xx (xx.xx)	XX.XX	XX.XX	XX.XX	XX.XX	XX.XX
		(xx.xx)	(xx.xx)	(xx.xx)	(xx.xx)	(xx.xx)
Raw p-value for intervention compared to control		X.XXX	X.XXX	X.XXX	X.XXX	X.XXX
Mean MUAC z-score (SD)	xx.xx (xx.xx)	XX.XX	XX.XX	XX.XX	XX.XX	XX.XX
		(xx.xx)	(xx.xx)	(xx.xx)	(xx.xx)	(xx.xx)
Raw p-value for intervention compared to control		x.xxx	X.XXX	X.XXX	X.XXX	X.XXX
Mean head circumference z-score (SD)	xx.xx (xx.xx)	XX.XX	XX.XX	XX.XX	XX.XX	XX.XX
		(xx.xx)	(xx.xx)	(xx.xx)	(xx.xx)	(xx.xx)
Raw p-value for intervention compared to control		X.XXX	X.XXX	X.XXX	x.xxx	X.XXX

Variable	Control	10g milk LNS	20g milk LNS	20g milk-free LNS	40g milk LNS	40g milk-free LNS
Change in weight, mean (SD),kg	x.xx (x.xx)	x.xx (x.xx)	x.xx (x.xx)	x.xx (x.xx)	x.xx (x.xx)	x.xx (x.xx)
Raw p-value for intervention compared to control		X.XXX	X.XXX	X.XXX	X.XXX	X.XXX
Difference in means (95% CI)		xxx (xx to xx)	xxx (xx to xx)	xxx (xx to xx)	xxx (xx to xx)	xxx (xx to xx)
Change in length, mean (SD), cm	x.xx (x.xx)	x.xx (x.xx)	x.xx (x.xx)	x.xx (x.xx)	x.xx (x.xx)	x.xx (x.xx)
Raw p-value for intervention compared to control		X.XXX	X.XXX	X.XXX	X.XXX	X.XXX
Difference in means (95% CI)		xxx (xx to xx)	xxx (xx to xx)	xxx (xx to xx)	xxx (xx to xx)	xxx (xx to xx)
Change in Middle upper arm circumference, mean (SD),cm	x.xx (x.xx)	x.xx (x.xx)	x.xx (x.xx)	x.xx (x.xx)	x.xx (x.xx)	x.xx (x.xx)
Raw p-value for intervention compared to control		X.XXX	X.XXX	X.XXX	X.XXX	X.XXX
Difference in means (95% CI)		xxx (xx to xx)	xxx (xx to xx)	xxx (xx to xx)	xxx (xx to xx)	xxx (xx to xx)
Change in Head circumference, mean (SD), cm	x.xx (x.xx)	x.xx (x.xx)	x.xx (x.xx)	x.xx (x.xx)	x.xx (x.xx)	x.xx (x.xx)
Raw p-value for intervention compared to control		X.XXX	X.XXX	X.XXX	X.XXX	X.XXX

Table 2 Anthropometric outcome changes during and up to 12 months of intervention

D	4.0	640	
Page	10	of 13	

Difference in means (95% CI)		xxx (xx to xx)				
Change in Weight-for-age z-score, mean (SD)	x.xx (x.xx)	x.xx (x.xx)	x.xx (x.xx)	x.xx (x.xx)	x.xx (x.xx)	x.xx (x.xx)
Raw p-value for intervention compared to control		X.XXX	x.xxx	x.xxx	X.XXX	X.XXX
Difference in means (95% CI)		xxx (xx to xx)				
Change in Length-for-age z-score mean (SD)	x.xx (x.xx)	x.xx (x.xx)	x.xx (x.xx)	x.xx (x.xx)	x.xx (x.xx)	x.xx (x.xx)
Raw p-value for intervention compared to control		X.XXX	X.XXX	X.XXX	X.XXX	X.XXX
Difference in means (95% CI)		xxx (xx to xx)				
Change in head circumference z- score mean (SD)	x.xx (x.xx)	x.xx (x.xx)	x.xx (x.xx)	x.xx (x.xx)	x.xx (x.xx)	x.xx (x.xx)
Raw p-value for intervention compared to control		X.XXX	X.XXX	X.XXX	X.XXX	X.XXX
Difference in means (95% CI)		xxx (xx to xx)				
Change in MUAC z-score mean (SD)	x.xx (x.xx)	x.xx (x.xx)	x.xx (x.xx)	x.xx (x.xx)	x.xx (x.xx)	x.xx (x.xx)
Raw p-value for intervention compared to control		X.XXX	X.XXX	X.XXX	X.XXX	X.XXX

Difference in means (95% CI)		xxx (xx to xx)				
Change in Weight-for-length z-score	x.xx (x.xx)	x.xx (x.xx)	x.xx (x.xx)	x.xx (x.xx)	x.xx (x.xx)	x.xx (x.xx)
mean (SD)						
Raw p-value for intervention		X.XXX	X.XXX	X.XXX	X.XXX	X.XXX
compared to control						
Difference in means (95% CI)		xxx (xx to xx)				

Variable	Control	10g milk	20g milk	20g milk-	40g milk	40g milk-	P-
		LNS	LNS	free LNS	LNS	free LNS	value
Proportion severe stunting (LAZ<-3), No. /total	xxx/xxx	xxx/xxx	xxx/xxx	xxx/xxx	XXX/XXX	xxx/xxx	X.XXX
No. (%)	(xx.x%)	(xx.x%),	(xx.x%),	(xx.x%), x.xx	(xx.x%),	(xx.x%),	
Deleting right (05% CI)		x.xx (x.xx-	x.xx (x.xx-	(x.xx-x.xx)	x.xx (x.xx-	x.xx (x.xx-	
Kelative fisk (95% CI)		x.xx)	x.xx)		x.xx)	x.xx)	
Proportion moderate to severe stunting (LAZ <-	xxx/xxx	xxx/xxx	xxx/xxx	xxx/xxx	xxx/xxx	xxx/xxx	X.XXX
2), No. /total No. (%)	(xx.x%)	(xx.x%),	(xx.x%),	(xx.x%), x.xx	(xx.x%),	(xx.x%),	
Deletion del (050/ CD)		x.xx (x.xx-	x.xx (x.xx-	(x.xx-x.xx)	x.xx (x.xx-	x.xx (x.xx-	
Relative risk (95% CI)		x.xx)	x.xx)		x.xx)	x.xx)	
Proportion severe underweight (WAZ <-3),	xxx/xxx	xxx/xxx	xxx/xxx	xxx/xxx	xxx/xxx	xxx/xxx	X.XXX
No. /total No. (%)	(xx.x%)	(xx.x%),	(xx.x%),	(xx.x%), x.xx	(xx.x%),	(xx.x%),	
Deletion del (050/ CD)		x.xx (x.xx-	x.xx (x.xx-	(x.xx-x.xx)	x.xx (x.xx-	x.xx (x.xx-	
Kelative fisk (95% CI)		x.xx)	x.xx)		x.xx)	x.xx)	
Proportion moderate to severe underweight	xxx/xxx	xxx/xxx	xxx/xxx	xxx/xxx	xxx/xxx	xxx/xxx	X.XXX
(WAZ <-2), No. /total No. (%)	(xx.x%)	(xx.x%),	(xx.x%),	(xx.x%), x.xx	(xx.x%),	(xx.x%),	
Deletion del (050/ CD)		x.xx (x.xx-	x.xx (x.xx-	(x.xx-x.xx)	x.xx (x.xx-	x.xx (x.xx-	
Relative risk (95% CI)		x.xx)	x.xx)		x.xx)	x.xx)	
Proportion severe wasting (WHZ <-3), No.	xxx/xxx	xxx/xxx	xxx/xxx	xxx/xxx	xxx/xxx	xxx/xxx	X.XXX
/total No. No. /total No. (%)	(xx.x%)	(xx.x%),	(xx.x%),	(xx.x%), x.xx	(xx.x%),	(xx.x%),	
		x.xx (x.xx-	x.xx (x.xx-	(x.xx-x.xx)	x.xx (x.xx-	x.xx (x.xx-	
Kelative risk (95% CI)		x.xx)	x.xx)		x.xx)	x.xx)	
Proportion moderate to severe wasting (WHZ <-	xxx/xxx	xxx/xxx	xxx/xxx	xxx/xxx	xxx/xxx	xxx/xxx	X.XXX
		(xx.x%),	(xx.x%),	(xx.x%), x.xx	(xx.x%),	(xx.x%),	

Table 3 Incidence of various forms of malnutrition at 18 months of age

2), No. /total No. (%)	(xx.x%)	x.xx (x.xx-	x.xx (x.xx-	(x.xx-x.xx)	x.xx (x.xx-	x.xx (x.xx-	
Relative risk (95% CI)		x.xx)	x.xx)		x.xx)	x.xx)	

Prevention of Linear Growth Faltering in Infants and Young Children With Lipid-based Nutrient Supplements (iLiNS-DOSE)

Statistical Analysis Plan

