Variable	Control	10g milk	20g milk	20g milk-	40g milk	40g milk-	Test
		LNS	LNS	free LNS	LNS	free LNS	
Number of participants	XXX	XXX	XXX	XXX	XXX	XXX	
Age, months (mean, SD, N)	xx.x (xx.x)	xx.x (xx.x)	xx.x (xx.x)	xx.x (xx.x)	xx.x (xx.x)	xx.x (xx.x)	ANOVA
Proportion of Males (percentage)	xxx / xxx (xx%)	xxx/ xxx (xx%)	Chi-squared				
Weight, kg (mean, SD, N)	xx.x (xx.x)	xx.x (xx.x)	xx.x (xx.x)	xx.x (xx.x)	xx.x (xx.x)	xx.x (xx.x)	ANOVA
Length, cm (mean, SD, N)	xx.x (xx.x)	xx.x (xx.x)	xx.x (xx.x)	xx.x (xx.x)	xx.x (xx.x)	xx.x (xx.x)	ANOVA
Middle upper arm circumference, cm (mean, SD, N)	xx.x (xx.x)	XX.X (XX.X)	XX.X (XX.X)	xx.x (xx.x)	xx.x (xx.x)	xx.x (xx.x)	ANOVA
Head circumference, cm (mean, SD, N)	xx.x (xx.x)	xx.x (xx.x)	XX.X (XX.X)	xx.x (xx.x)	XX.X (XX.X)	xx.x (xx.x)	ANOVA
Weight-for-age z-score (mean, SD, N)	xx.xx (xx.xx)	XX.XX (XX.XX)	XX.XX (XX.XX)	xx.xx (xx.xx)	xx.xx (xx.xx)	xx.xx (xx.xx)	ANOVA
Length-for-age z-score (mean, SD, N)	xx.xx (xx.xx)	XX.XX (XX.XX)	XX.XX (XX.XX)	xx.xx (xx.xx)	xx.xx (xx.xx)	xx.xx (xx.xx)	ANOVA
Weight-for-length z-score (mean,	xx.xx (xx.xx)	XX.XX (XX.XX)	XX.XX (XX.XX)	xx.xx (xx.xx)	xx.xx (xx.xx)	xx.xx (xx.xx)	ANOVA

SD, N)							
MUAC z-score (mean, SD, N)	XX.XX (XX.XX)	XX.XX (XX.XX)	xx.xx (xx.xx)	xx.xx (xx.xx)	xx.xx (xx.xx)	xx.xx (xx.xx)	ANOVA
Head circumference z-score (mean, SD, N)	xx.xx (xx.xx)	xx.xx (xx.xx)	xx.xx (xx.xx)	xx.xx (xx.xx)	xx.xx (xx.xx)	xx.xx (xx.xx)	ANOVA
Incidence of severe stunting at 6	xxx / xxx	xxx/ xxx	xxx/ xxx	xxx/ xxx	xxx/ xxx	xxx/ xxx	Fisher's
months of age (percentage)	(xx%)	(xx%)	(xx%)	(xx%)	(xx%)	(xx%)	exact test
Incidence of moderate and severe	xxx / xxx	xxx/ xxx	xxx/ xxx	xxx/ xxx	xxx/ xxx	xxx/ xxx	Fisher's
stunting at 6 months of age	(xx%)	(xx%)	(xx%)	(xx %)	(xx%)	(xx %)	exact test
(percentage)							
Blood hemoglobin concentration	xx.x (xx.x)	xx.x (xx.x)	xx.x (xx.x)	xx.x (xx.x)	xx.x (xx.x)	xx.x (xx.x)	ANOVA
g/dl (mean, SD, N)							
Proportion of participants with	xxx / xxx	xxx/ xxx	xxx/ xxx	xxx/ xxx	xxx/ xxx	xxx/ xxx	Chi-squared
anaemia (percentage)	(xx%)	(xx%)	(xx%)	(xx%)	(xx%)	(xx%)	
ZPP concentration $\mu g/g$ (mean, SD,	xx.x (xx.x)	xx.x (xx.x)	xx.x (xx.x)	xx.x (xx.x)	xx.x (xx.x)	xx.x (xx.x)	ANOVA
N)							
ZPP concentration >45 (percentage)	xxx / xxx	xxx/ xxx	xxx/ xxx	xxx/ xxx	xxx/ xxx	xxx/ xxx	Chi-squared
	(xx%)	(xx%)	(xx%)	(xx%)	(xx%)	(xx%)	

Table 1b Other baseline characteristics to be assessed

Variable	Control	10g milk LNS	20g milk	20g milk-free	40g milk	40g milk-	Test

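### Appendix 1 carries over the covariates chosen for change in LAZ, so adjustment for the outcome's own 6-month value is not guaranteed for MUAC-for-age, head-circumference-for-age or WAZ; the cost is precision, not bias

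*SAP*

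**What the plan says.** Appendix 1, section 7.6, reads in full: "The same adjustments will be done as for the main analyses".

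The main SAP, section 12.6, defines four models for change in LAZ. Model 1 is unadjusted, model 2 adds the 6-month LAZ, and model 3 has the 6-month WHZ in its place. Model 4 is set out as "Adjustment for baseline LAZ-score and baseline WHZ-score and for any of the variables presented in tables 1a and 1b showing statistically significant association". The yardstick for entry to model 4 is stated as "at p<0.1 level) with the change in LAZ-score".

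If any model moves the group coefficient by more than 10% from the unadjusted one, adjusted results take priority in publication. Otherwise the tables are unadjusted and model 4 is reported in the text.

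Appendix 1, section 6.1, has the 18-month values and the changes in each intervention group "individually compared against that of the control group using a two-sample t-test", with conclusions resting on Holm-adjusted p-values. Hypothesis 1 of Appendix 1 concerns the changes in WAZ, WHZ, MUAC-for-age and head-circumference-for-age Z-scores.

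Table 1a of the main SAP lists the relevant baselines, for example "MUAC z-score (mean, SD, N"), together with the head circumference and weight-for-age Z-scores.

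**The concern.** For the primary outcome, model 2 adjusts for the outcome's own baseline. Copied unchanged to the secondary growth outcomes, that property survives only for LAZ (models 2 and 4) and WHZ (models 3 and 4). For MUAC-for-age, head-circumference-for-age and WAZ, the guaranteed covariates are baselines of other measures. The own baseline enters only if it happens to be associated with change in LAZ, which is not the outcome being analysed.

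The own 6-month value is usually the strongest single predictor of an 18-month anthropometric value, and it is already collected. Leaving its use to chance gives up precision in the five comparisons with control for each outcome. The 10% rule inherits the problem: for these outcomes, models 2 and 3 decide whether adjusted results are presented on the basis of covariates that are not the natural baseline.

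**Working it through.** **Step 1: where the own baseline can enter.**

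| Outcome | Model 1 | Model 2 | Model 3 | Model 4 |
|---|---|---|---|---|
| WHZ | no | no | yes | yes |
| WAZ | no | no | no | only by screen |
| MUAC-for-age Z | no | no | no | only by screen |
| Head-circumference-for-age Z | no | no | no | only by screen |

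**Step 2: how likely the screen is to admit it.** With N children, p<0.1 requires |r| > t/√(N−2+t²), where t is the 95th percentile of the t distribution. At N = 1932 (the number enrolled) this is about 0.037. With assumed losses of 15% and 25% (N = 1642 and 1449) it is 0.041 and 0.043. The hurdle is low, so entry is quite possible, but it depends on a correlation with change in LAZ that is unknown in advance.

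If the screen were instead run against the outcome's own change, the correlation of baseline with change would be −√((1−ρ)/2), where ρ is the 6-to-18-month correlation. That is −0.50 at ρ = 0.5 and −0.39 at ρ = 0.7, with |t| about 25 and 18 at N = 1932. The own baseline would then practically always enter.

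**Step 3: what own-baseline adjustment is worth.** The SAP gives no SD, correlation or power for these outcomes, so there is no stated figure to reproduce. Assumptions: equal SDs at both visits and ρ between 0.5 and 0.8. With SD 1 and n per arm, the variance of one contrast with control is:

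- 18-month value: 2/n
- change: (2/n) × 2(1−ρ)
- regression on own baseline (ANCOVA): (2/n) × (1−ρ²)

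The variance ratio k against ANCOVA is 2/(1+ρ) for the change and 1/(1−ρ²) for the 18-month value. A test with 80% power at two-sided 5% has an expected z of 1.96 + 0.84 = 2.80. With ANCOVA its power becomes Φ(2.80√k − 1.96).

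| ρ | k, change | Change test, 80% becomes | k, 18-month value | 18-month test, 80% becomes |
|---|---|---|---|---|
| 0.5 | 1.33 | 90% | 1.33 | 90% |
| 0.6 | 1.25 | 88% | 1.56 | 94% |
| 0.7 | 1.18 | 86% | 1.96 | 97.5% |
| 0.8 | 1.11 | 84% | 2.78 | 99.7% |

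These ratios do not depend on n.

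**Step 4: the same on the trial's scale.** With 1932/6 = 322 per arm (equal arms assumed, before losses), √(2/322) = 0.0788. At ρ = 0.7 the difference detectable with 80% power is:

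- 18-month value: 2.80 × 0.0788 = 0.22 SD
- change: 0.22 × √0.6 = 0.17 SD
- ANCOVA: 0.22 × √0.51 = 0.16 SD

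For an assumed true difference of 0.2 SD, power for 18-month value, change and ANCOVA is 72%, 72% and 83% at ρ = 0.5, and 72%, 91% and 94% at ρ = 0.7. All figures are for one comparison before Holm.

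**The case against.** The strongest case against has four parts.

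- **The own baseline is not excluded.** A reader might infer that MUAC and head circumference are never adjusted for their own baseline. The SAP does not support that: their baselines are in Table 1a and can enter model 4. What stands is that entry is not guaranteed and that the screen is written for another outcome.
- **There is no bias.** A reader might infer that the change score over-corrects, or that the 18-month comparison is distorted by baseline imbalance. Under random allocation the 18-month, change and ANCOVA contrasts all estimate the same mean difference without bias, leaving losses to follow-up aside. The change-score t-test is valid and is also the primary LAZ method in section 11.3. This objection stands in full.
- **The hypothesis is about change.** The baseline is therefore already subtracted, and the large gains for the 18-month values belong to the less relevant test. This also stands: the change column is the one to quote, and its gain shrinks as ρ rises.
- **Section 7.6 may mean the same procedure applied to each outcome.** On that reading the own baseline would almost always enter model 4. The wording does not say so, however. Appendix 2, section 6.6, expressly screens against the developmental score, and the sensitivity model in Appendix 4, section 7.7, screens against physical activity. Appendix 1 makes no such change. Even on the generous reading, the deciding t-tests remain unadjusted.

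**Conclusion.** The point holds as a gap in specification with a cost in precision. Appendix 1 guarantees own-baseline adjustment for WHZ but not for WAZ, MUAC-for-age or head-circumference-for-age, and its covariate screen is tied to change in LAZ.

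For the hypothesised change outcomes, the assumed range implies a rise from 80% power to between 90% (ρ = 0.5) and 84% (ρ = 0.8). For the 18-month values the gain is equal at ρ = 0.5 and larger above it. Both gains are measured against the unadjusted tests. The gain over models 2 to 4 cannot be computed, because the SAP gives no correlations between baseline measures. For WAZ in particular, baseline LAZ and WHZ may carry some of the same information, but the documents do not show how much.

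The outcomes are secondary, and the existing tests are valid. The change is worth making because it is nearly free and removes a choice that would otherwise depend on an irrelevant screen.

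**What to change.** Replace the sentence in Appendix 1, section 7.6, with wording such as:

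*Each continuous anthropometric outcome is compared by linear regression on intervention group, always including the 6-month value of the same measure. Any further covariates are screened against that outcome and not against change in LAZ. Holm-adjusted conclusions are drawn from this model; the t-tests in Tables 1 and 2 are supporting results.*

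Amend section 6.1 to match. With the 6-month value in the model, the group effect is the same whether the dependent variable is the 18-month value or the change, so one model serves both tables.

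The cost is SAP wording and one covariate. No new data are needed. The change analysis loses no children, because it already requires both visits; an 18-month comparison would lose any child without a valid 6-month value.

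Appendix 7, section 2, already reports the linear growth result. The amendment should therefore be dated, and if the Appendix 1 comparisons have been run, the new model should be labelled as added afterwards.
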